10.3. Effectiveness analysis

Data name	Derivation and calculation methods	
Remission	When the CDAI score is <150, the case is regarded as remission.	
WPAI	
Q1 Do you work now? Yes, no
 
Q2 How many hours did you leave the work due to problems related to Crohn's disease over the past 7 days? () hour(s)
 
Q3 How many hours did you leave the work for a reason other than Crohn's disease such as holidays or hours for which you were off to participate in this survey over the past 7 days? () hour(s)
 
Q4 How many hours did you actually work for the past 7 days? () hour(s)
 
Q5 How much productivity was affected by Crohn's disease while you were working over the past 7 days? 0: Crohn's disease did not affect the work. 10: Crohn's disease completely interrupted the work. Based on the above, your score between 0 to 10. ()
 
Q6 How much did Crohn's disease affect various daily activities except your job over the past 7 days? ()
	

Data name	Derivation and calculation methods		
		
0: Crohn's disease did not affect daily activities.
 
10: Crohn's disease completely interrupted daily activities.
 
Based on the above, your score between 0 to 10.
	

- Absenteeism (%)

Calculate it with the following formula based on the questions (Q1 to Q6) on the above table:

$$[Q2 / (Q2 + Q4)] \times 100$$

- Presenteeism (%)

Calculate it with the following formula based on the questions (Q1 to Q6) on the above table:

$$(Q5 / 10) \times 100$$

- Overall work impairment (%)

Calculate it with the following formula based on the questions (Q1 to Q6) on the above table:

$$\{ Q2 / (Q2 + Q4) + [1 - Q2 / (Q2 + Q4)] \times (Q5 / 10) \} \times 100$$

- Activity Impairment (%)

Calculate it with the following formula based on the questions (Q1 to Q6) on the above table:

$$(Q6 / 10) \times 100$$

11. How to stratify data

Data	How to stratify
Dosage and administration	160mg→80mg→40mg once every two weeks, other
Dosing frequency (times)	≥1 and <4, ≥4 and <13, ≥13 and <26, ≥26 and <39, ≥39 and <52, ≥52 and <65, ≥65 and <78, ≥78
Total dose (mg)	<500mg, ≥500mg and <1000mg ≥1000mg and <2000mg ≥2000mg and <3000mg ≥3000mg, Unknown

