12.1. Assessment period for CDAI, WPAI, CRP and non-intestinal conditions

Time allowance of assessment period with the first administration date of Humira as 1 is as follows:

Assessment period	Time Allowance(Day)
At the first administration	- 1 (scheduled date 1)
Week 4 of administration	15 - 43 (scheduled date 29)
Month 3 of administration	71 - 99 (scheduled date 85)
Month 6 of administration	169 - 197 (scheduled date 183)
Year 1 of administration	337 - 393 (scheduled date 365)
Year 1 and Month 6 of administration	519 - 575 (scheduled date 547)
Year 2 of administration	701 - 757 (scheduled date 729)
Year 2 and Month 6 of administration	883 - 939 (scheduled date 911)
Year 3 of administration	1065 - 1121 (scheduled date 1093)
At final assessment	Final assessment of each patient no matter whether the each assessment period is within Time Allowance.

The data for analysis should derive from the date closest to the scheduled date within Time Allowance. If there are more than one data dated on the same day, select the worst value.

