Note: Follow “12.1 Assessment period for CDAI, WPAI, CRP and non-intestinal conditions” for Time Allowance of the final assessment periods. The analysis covers only the patients with the assessment at the first administration and thereafter.

“3.2.2.1 Changes in the remission rate at each point (CDAI<150) (Observed Case)”

Patients for analysis: patients in the effectiveness analysis group

Analysis objective: to show the remission rate of CDAI at each assessment period.

Analysis item: Calculate the number of target patients, the percentage to the number of patients who achieved a remission and the number of target patients, 95%CI of the remission rate, and conduct a McNemar test for the first administration per assessment period.

Note: Follow “12.1 Assessment period for CDAI, WPAI, CRP and non-intestinal conditions” for Time Allowance of the final assessment periods. The analysis covers only the patients with the assessment at the first administration and thereafter.

For the confidence interval, use the Clopper-Pearson’s confidence interval.

“3.2.2.3 Changes in the remission rate at each point (CDAI<150) (Observed Case)”

Patients for analysis: the patients in the effectiveness analysis group whose CDAI was a remission (≥ 150) after they were started on Humira.

Analysis objective: to show the remission rate of CDAI at each assessment period of patients whose CDAI failed to achieve a remission when the administration was started.

Analysis item: Calculate the number of target patients, the percentage to the number of patients who achieved a remission and the number of target patients, 95%CI of the remission rate, and conduct a McNemar test for the first administration per assessment period.

Note: Follow “12.1 Assessment period for CDAI, WPAI, CRP and non-intestinal conditions” for Time Allowance of the final assessment periods. The analysis covers only the patients with the assessment at the first administration and thereafter.

For the confidence interval, use the Clopper-Pearson’s confidence interval.

“3.2.4.2 Endoscopy results during administration (small intestine: active phase/remission phase)”

Patients for analysis: patients in the effectiveness analysis group

Analysis objective: to show endoscopy results (small intestine) at each assessment period.

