Note: Follow “12.2 Assessment period for endoscopy results” for Time Allowance of assessment period. The analysis covers only the patients with the data showing that endoscopy for small and large intestines was done on the same day at the first administration and thereafter in the effectiveness analysis group.

“3.2.6.2 Changes in WPAI:CD since the administration was started (Observed Case)”

Patients for analysis: patients in the effectiveness analysis group

Analysis objective: to show WPAI at each assessment period.

Analysis items: Calculate the number of target patients and the summary statistics of WPAI for each assessment period, and conduct a paired-t test which compares the values at the initial administration.

Note: Follow “12.1 Assessment period for CDAI, WPAI, CRP and non-intestinal conditions” for Time Allowance of the final assessment periods. The analysis covers only the patients with the WPAI assessment at the first administration and thereafter in the effectiveness analysis group.

“3.2.7.2 Changes in CRP level since the administration was started (Observed Case)”

Patients for analysis: patients in the effectiveness analysis group

Analysis objective: to show CRP levels at each assessment period.

Analysis items: Calculate the number of target patients and the summary statistics of CRP for each assessment period, and conduct a paired-t test which compares the values at the initial administration.

Note: Follow “12.1 Assessment period for CDAI, WPAI, CRP and non-intestinal conditions” for Time Allowance of the final assessment periods. The analysis covers only the patients with the CRP assessment at the first administration and thereafter in the effectiveness analysis group.

“3.2.7.3 Remission rate at the final assessment in patients who achieved a remission of CDAI at Week 4 of administration”

Patients for analysis: Patients in the effectiveness analysis group (the patients who did not achieve a remission (≥ 150) when the administration was started but achieved the remission (< 150) at Week 4 of administration in CDAI)

Patients for analysis: to show the remission rate of CDAI at the final assessment regarding the patients who did not achieve a remission (≥ 150) when the administration was started but achieved the remission (< 150) at Week 4 of administration.

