Analysis items: calculate the number of target patients, the percentage to the number of patients who achieved a remission at the final assessment and the target patients, and the 95% confidence interval of the remission rate.

Note: The target patients need to have their CDAI measured at 3 time points or more, that is, at the first administration, Week 4 of administration and any point after Week 4 of administration and also have a record that they did not achieve a remission (≥ 150) at the first administration but achieved the remission (< 150) at Week 4 of administration.

Follow “12.1 Assessment period for CDAI, WPAI, CRP and non-intestinal conditions” for Time Allowance of the assessment periods.

For the confidence interval, use the Clopper-Pearson's confidence interval.

“3.2.8 Subsequent changes in the conditions of patients with non-intestinal conditions observed at the first administration (Observed Case)”

Patients for analysis: patients in the effectiveness analysis group

Analysis objective: to show the conditions at each assessment period regarding non-intestinal conditions observed at the first administration.

Analysis item: Calculate the number of target patients, the percentage to the number of patients with the conditions and the number of target patients, and conduct a McNemar test for the first administration per assessment period.

Note: The analysis covers only the patients with the assessment at the first administration and thereafter as well as the patients with symptoms for each “arthritis/arthralgia”, “iritis/uveitis”, and “erythema nodosum/gangrenous abscess/aphthous stomatitis” at the first administration.

To analyze “with any of non-intestinal conditions”, the patients with any symptom at each assessment period regarding any of the items answered as ‘with a symptom’ at the first administration are regarded as the patients with conditions. When a patient had multiple symptoms at the first administration, they should be regarded as “with conditions” if any of the symptoms persisted. Do not include in analysis the items in which no symptoms were observed at the first administration. (Do not include in the analysis a symptom which first developed at an assessment

period after the first administration, either)

Follow “12.1 Assessment period for CDAI, WPAI, CRP and non-intestinal conditions” for Time Allowance of the assessment periods.

“3.4.1 Aggregation for effectiveness per patient background factor (CDAI)”

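### Tables 3.2.2.3 and 3.2.8 run McNemar tests in patients who all share one baseline state, so one discordant cell is zero by construction

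*SAP*

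**What the plan says.** SAP 10.3 defines remission: "When the CDAI score is <150, the case is regarded as remission".

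**Table 3.2.2.3** (SAP 13.3). The objective line is to show the "remission rate of CDAI at each assessment period of patients whose CDAI failed to achieve a remission when the administration was started". At each assessment period it plans the remission rate, a Clopper-Pearson 95% interval and a McNemar test against the first administration. Its population line reads differently: patients "whose CDAI was a remission (≥ 150) after they were started on Humira". Table 3.2.1.2 has the same population line.

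**Table 3.2.8** (SAP 13.3). It covers patients with a given non-intestinal symptom at the first administration, in three symptom groups plus a row for any of them. The instruction is to give the percentage of "patients with the conditions and the number of target patients, and conduct a McNemar test for the first administration per assessment period". The note adds: "Do not include in analysis the items in which no symptoms were observed at the first administration". Symptoms that first appear later are also left out. No confidence interval is planned.

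**Tables for comparison.** Table 3.2.2.1 runs the same McNemar test in the whole effectiveness group. Table 3.2.7.3 takes patients not in remission "when the administration was started but achieved the remission" by Week 4, and reports those "who achieved a remission at the final assessment and the target patients, and the 95% confidence interval of the remission rate", with no test.

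**Testing rules.** SAP 9.6 sets a two-sided 5% level and calls p below 0.05 significant. SAP 9.5 makes no multiplicity adjustment. The SAP does not say whether McNemar is exact, uncorrected or continuity-corrected.

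**The concern.** McNemar's test asks whether changes in one direction are as frequent as changes in the other. That question needs patients who could move either way. In these two tables everyone starts in the same state, so movement in one direction is impossible. The null hypothesis is then untrue unless no patient can ever change, and any significant result must favour improvement. Ordinary fluctuation around the CDAI cut-off of 150, or natural resolution of a symptom, is enough to produce one.

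The SAP attaches the word significant to p below 0.05, and SAP 3.1 says the results feed the regulatory report and the re-examination application. A reader could take these p-values as evidence of effectiveness, which they cannot supply. In table 3.2.8 the p-value is the only inferential result shown.

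**Working it through.** The SAP gives no sample size, expected rate or p-value for these tables, so there is no stated figure to reproduce.

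**1. The zero cell.** For table 3.2.2.3, read by its objective line, with n patients of whom b are in remission later:

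| At first administration | Later: remission | Later: no remission |
|---|---|---|
| No remission | b | n − b |
| Remission | c = 0 | 0 |

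The second row is empty because patients in remission at baseline are excluded. In table 3.2.8 the row for symptom-free at baseline is empty for the same reason. This includes the row for any condition, which counts only symptoms present at baseline. Here b is the number whose symptom has resolved.

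**2. The p-value with c = 0.**
- Uncorrected: chi-square = (b − c)²/(b + c) = b. For b = 3, p = 0.083; for b = 4, p = 0.0455.
- Continuity-corrected: chi-square = (b − 1)²/b. For b = 5, p = 0.074; for b = 6, 25/6 = 4.17 and p = 0.041.
- Exact two-sided: p = 2 × 0.5^b. For b = 5, p = 0.0625; for b = 6, p = 0.031.

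So p < 0.05 needs four improvers (uncorrected) or six (corrected or exact), whatever the group size.

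**3. What six improvers mean.** The exact p is 0.031 in every row:

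| Improvers / n | Rate | Clopper-Pearson 95% |
|---|---|---|
| 6/10 | 60% | 26.2–87.8% |
| 6/50 | 12% | 4.5–24.3% |
| 6/200 | 3% | 1.1–6.4% |

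**4. How often change without any drug effect would reach the threshold.** The documents give neither subset sizes nor spontaneous change rates. Both are assumed here, with binomial tails:

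| n (assumed) | Change rate (assumed) | P(b ≥ 4) | P(b ≥ 6) |
|---|---|---|---|
| 10 | 10% | 0.013 | <0.001 |
| 30 | 10% | 0.353 | 0.073 |
| 50 | 10% | 0.750 | 0.384 |
| 100 | 5% | 0.742 | 0.384 |
| 200 | 5% | 0.991 | 0.938 |

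Small rows of table 3.2.8 may rarely reach significance; large groups usually would.

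**5. Selected against unselected.** A simulation with no mean change in CDAI was run with 300 patients, SD 80, mean 180 or 220, and correlation 0.5, 0.7 or 0.9 between visits (all assumed; 2,000 runs each). The exact test rejected in 3.2–3.5% of runs in the full group, and in 99.7–100% of runs among those with baseline CDAI of 150 or more. The selection produces the difference.

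**6. Number of tests.** SAP 12.1 lists eight post-baseline windows plus the final assessment, which makes 9. Table 3.2.2.3: 1 × 9 = 9. Table 3.2.8: (3 symptom groups + any) × 9 = 36. Total: up to 45.

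**The case against.** The strongest case against acting is that little rests on these p-values. This is a single-arm survey aimed at malignancy and serious infection, and no sample size or success criterion depends on either table. In table 3.2.2.3 the rate and its exact interval stand beside the p-value, so a reader would see that 6/200 is 3%. This limits the harm and is accepted. It does not make the test informative, and table 3.2.8 has no interval to offset it.

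Second, every McNemar p-value ignores concordant pairs, so indifference to group size is not peculiar to these tables. That is correct. The 6/10, 6/50 and 6/200 comparison shows how little a significant result would mean; the defect itself is that c is fixed at zero.

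Third, no uncontrolled before-after test separates drug effect from regression to the mean, including the paired t-test of table 3.2.1.2 in the same selected group. Also correct. The difference is that a patient's CDAI can rise as well as fall after baseline, so a null of zero mean change is possible there. That test is biased but not degenerate, and a stated limitation can cover it.

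Fourth, table 3.2.7.3 is only a loose precedent, since it also selects on Week 4 status and reports one time point. It shows that a rate with an interval is workable, not that the SAP recognised this problem.

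Fifth, if the population line of table 3.2.2.3 were applied literally, to CDAI after the start of treatment, the zero cell would not follow there. Nothing else supports that reading: it contradicts SAP 10.3, the table's own objective and the wording of 3.2.7.3. The point on table 3.2.8 does not depend on it.

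**Conclusion.** The concern holds. In table 3.2.8 the zero cell follows directly from the note. In table 3.2.2.3 it follows from the objective line together with the definition of remission. The planned p-values, up to 45, reflect only how many patients improved and can be significant only in favour of treatment; four or six improvers suffice, depending on the unspecified version of the test.

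The structural result and the thresholds need no assumptions. How often significance would arise from fluctuation alone does depend on assumed group sizes and change rates, and ranges from negligible in very small rows to near certain in large groups.

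The consequence is limited to supplementary effectiveness p-values, but the SAP should be corrected. The contradictory population lines in 3.2.1.2 and 3.2.2.3 are a separate wording error and need correcting in any case, because they determine who enters those tables.

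**What to change.** - **Table 3.2.2.3:** delete the McNemar test; report the remission rate with the Clopper-Pearson interval already planned.
- **Table 3.2.8:** delete the McNemar test; report the proportion whose baseline symptom persists (or has resolved) with an exact 95% interval.
- **Table 3.2.2.1:** keep McNemar here, where both discordant cells can be filled, and state which version is used.
- **Tables 3.2.1.2 and 3.2.2.3, population line:** change to patients with CDAI ≥ 150, that is not in remission, at the first administration.
- **Table 3.2.1.2:** the paired t-test may stay, with regression to the mean noted as a limitation.

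The cost is SAP wording and minor programming: one test removed from each of two tables, one interval added and two population lines corrected. No new data are needed, and the only loss is up to 45 uninformative p-values.

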Detailed classification of prior treatment for Crohn's disease	Surgery, GCAP, enteral nutrition therapy, intravenous nutrition therapy, others
Treatment history with anti-TNF α drug	Without the history, with the history, unknown/not provided
Reason for discontinuation of treatment history with anti-TNF α drug	Lack of efficacy, adverse events, others, unknown/not provided
Concomitant medication	Without the history, with the history, unknown/not provided
Detailed classification	Aminosalicylic acid products, corticosteroid, immunosuppressant,

Data	How to stratify
of concomitant medications	antibiotics, and others
Concomitant therapy for Crohn's disease	Without the history, with the history, unknown/not provided
Detailed classification of concomitant therapy for Crohn's disease	Surgery, GCAP, enteral nutrition therapy, intravenous nutrition therapy, others
Condition/site of disease in the medical history of Crohn's disease	Anus/perianal region, rectum, stomach/duodenum, colon, jejunum/ileum, other, unknown/not provided
Intestinal complications as condition/site of disease in the medical history of Crohn's disease	Without the history, with the history, unknown/not provided
Non-intestinal complications as condition/site of disease in the medical history of Crohn's disease	Without the history, with the history, unknown/not provided
Work condition	Routinely engaged in wage labor for 35 hours or longer a week, Routinely engaged in wage labor for 35 hours or less a week, Not engaged in wage labor but do housework, shopping, childrearing, exercise, or study , Involved in daily living activities, Involved in less daily activities due to hospitalization, etc. Unknown/not provided
CDAI at the first administration	<150: remission ≥150 and <220: mild ≥220 and <450: moderate ≥450: severe Unknown/not provided
CRP	<1.0mg/dL, ≥1.0mg/dL,

Data	How to stratify
	Unknown/not provided
Self administration	Without the history, with the history, unknown/not provided

12. Data handling at test/assessment periods

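### SAP charts 3.2.2.3 and 3.2.1.2 select patients on one baseline CDAI of 150 or more, so regression to the mean alone yields some remitters and a fall in mean CDAI

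*SAP*

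**What the plan says.** SAP section 10.3 defines the response: "When the CDAI score is <150, the case is regarded as remission". No minimum fall and no second reading is required.

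SAP section 12.1 keeps one reading per assessment window: "The data for analysis should derive from the date closest to the scheduled date within Time Allowance". The only tie rule covers duplicates on one date: "If there are more than one data dated on the same day, select the worst value". The baseline value is likewise one reading, dated up to Day 1.

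By its objective line, chart 3.2.2.3 (SAP section 13.3) is to show the "remission rate of CDAI at each assessment period of patients whose CDAI failed to achieve a remission when the administration was started". The objective line of chart 3.2.1.2 restricts it to the same group, "patients whose CDAI failed to achieve a remission when the administration was started", that is, CDAI of 150 or more. Chart 3.2.2.3 reports the rate below 150 at each period, with a Clopper-Pearson interval and a McNemar test against the first administration. Chart 3.2.1.2 reports mean change with a paired t-test.

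SAP section 11 has a baseline band directly above the cut-off: "≥150 and <220: mild". Protocol section 3 sets no CDAI entry criterion, so patients close to 150 can be in the group.

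The population lines of both charts describe the group differently from the objective lines. I follow the objective lines here; that wording conflict is a separate point.

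**The concern.** The cut-off for entering the group and the cut-off for counting as a remitter are the same number, and each is judged on one reading. CDAI varies from visit to visit. Some patients enter because their baseline reading happened to be high, and their next reading tends to be lower. A patient at 155 who later reads 145 is a remitter.

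Baseline remission in this group is 0% by construction, so any crossing appears as a gain. The survey has no comparator to show how much of the gain would have occurred anyway. Chart 3.2.2.3 is the one most easily taken as remission gained on treatment, and the SAP feeds the re-examination application. In chart 3.2.1.2 the paired t-test has a null of zero mean change, but the selection makes the expected change negative even with no treatment effect.

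**Working it through.** **Inputs from the documents.** Remission cut-off 150 (SAP 10.3); one reading per window (12.1); selection at 150 or more (13.3, objective lines); bands 150 to <220, 220 to <450 and 450 or above (11); two-sided 5% level (9.6). The documents state no CDAI mean, SD, correlation or expected remission rate, so there is no planned figure to reproduce.

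**Assumed inputs, with no true change over time.**
- Setting A: readings are normal with the same mean μ and SD σ at every visit and correlation ρ between visits; μ 175-250, σ 80-100, ρ 0.5-0.9.
- Setting B: a true score (mean 180-250, SD 80-100, floored at 0) plus independent visit noise with SD 30-60; simulated.

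**Formulas for setting A.** With c = (150 − μ)/σ, Φ and φ the normal distribution function and density, and Φ2 the bivariate normal probability:
- No-effect remission rate = [Φ(c) − Φ2(c, c; ρ)] / [1 − Φ(c)].
- No-effect mean change = −(1 − ρ) σ φ(c) / [1 − Φ(c)].

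**Worked case: μ = 200, σ = 80, ρ = 0.7.**
- c = −50/80 = −0.625, Φ(c) = 0.266, Φ2 = 0.163.
- Remission rate = (0.266 − 0.163)/(1 − 0.266) = 0.103/0.734 = 14.0%.
- Mean change = −0.3 × 80 × 0.328/0.734 = −10.7 points.
- The SD of the change in the selected group is √[(1 − ρ)² Var(X | X ≥ 150) + σ²(1 − ρ²)] = √(0.09 × 3332 + 6400 × 0.51) = 59.7. With an assumed 150 patients the standard error is 59.7/√150 = 4.87, so the expected t is about 10.7/4.87 = 2.2. The test then declares improvement in about 59% of no-effect samples, against a nominal 2.5% in that direction.

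**Ranges for the whole selected group.**
- Remission rate per visit: 3.6-26.9% in A, 4.9-21.5% in B.
- Mean fall: 1.6-32.3 points in A, about 3-22 in B.
- Paired t-test significant towards improvement at 150 patients: 11-92% of no-effect samples in B.

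**Does banding help the remission rate?** In the worked case, with d = (220 − 200)/80 = 0.25 and Φ2(c, d; 0.7) = 0.245:
- 150 to <220: (0.2453 − 0.1630)/(0.5987 − 0.2660) = 24.7%.
- 220 or above: (0.2660 − 0.2453)/0.4013 = about 5%.

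In B the rate is about 18-34% in the 150 to <220 band and 0.5-12.0% at 220 or above, and 64-94% of no-effect remitters come from the lower band. The 12% is not a ceiling. At the most variable corner of A (μ = 175, σ = 100, ρ = 0.5) the rate at 220 or above is (0.4013 − 0.3400)/0.3264 = about 19%.

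**Does banding help the mean change?** No. In B with mean 220, SD 90 and visit SD 45, the built-in change is −8.4 points for the whole group, −16.0 at 220 or above, about −52 at 450 or above, and +6.7 (apparent worsening) at 150 to <220. A more extreme selection gives more regression to the mean.

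**The case against.** The strongest reply is that this is a descriptive survey and much of what is needed is already planned. Charts 3.1, 3.2.1.1 and 3.2.2.1 use the unselected group, where under no change the expected rate and mean do not move. Chart 3.4.1 tabulates final remission by baseline CDAI. No text claims that 3.2.2.3 measures a drug effect, and all the figures above rest on assumed distributions.

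Part of this stands. The unselected charts do avoid this selection effect, and the size cannot be read from the documents. But those charts do not repair the selected ones. Chart 3.4.1 covers only the final assessment and gives no interval. A 5% test is attached to both selected charts.

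A reader might infer three stronger things that the documents do not support:
- **That a patient counts as a remitter if ever below 150.** Under setting A an ever rule over eight visits would give about 12-72%, but section 12.1 uses one reading per period.
- **That chart 3.2.7.3 is inflated in the same way.** It covers "the patients who did not achieve a remission (≥ 150) when the administration was started but achieved the remission (< 150) at Week 4", so it selects on two readings. Noise pulls its final rate down from 100% at Week 4 (25-48% under no change in A). The bias is opposite, and requiring confirmation at Month 3 would change the question that the chart asks.
- **That the remission observed will be mostly noise.** The calculation shows what noise alone could produce. It says nothing about the true treatment effect.

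**Conclusion.** The concern holds for charts 3.2.2.3 and 3.2.1.2 as their objective lines describe them. The mechanism follows from the SAP's own definitions, and nothing in either document corrects for it.

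Under the assumed ranges the no-effect remission rate is about 4-27% per visit and the built-in mean fall about 2-32 points. Both are conditional on the assumed mean, SD and within-patient variability. The direction favours the drug in both charts. Most of the false remission sits in the 150 to <220 band. At 220 or above the rate is about 0.5-12% with visit SD 30-60, and higher if readings are less stable. The point does not extend to 3.2.7.3, and it would remain after the population wording and the McNemar test are dealt with.

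**What to change.** 1. **Chart 3.2.2.3.** Report the visit-wise remission rate with its Clopper-Pearson interval separately for baseline CDAI 150 to <220, 220 to <450, and 450 or above. Base interpretation on the bands at 220 or above, and state that this reduces regression to the mean but does not remove it. First reconcile the upper edge: section 11 puts a score of exactly 450 in severe, while chart 2.3 item (10) puts it in moderate.
2. **Chart 3.2.1.2.** Drop the paired t-test in the group selected on 150 or more, and keep it in the unselected chart 3.2.1.1. Do not present mean change by band as a correction, because banding enlarges the artefact in the higher bands.
3. **Optional in 3.2.2.3.** Add a row for CDAI below 150 at two consecutive scheduled assessments. In setting A this lowers the no-effect rate from 3.6-26.9% to 1.5-12.1%. It needs two observed visits, and a first reading below 150 at Year 3 cannot be confirmed. Do not add this requirement to 3.2.7.3.

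The cost is SAP wording and a few table rows from data already collected, with smaller numbers and wider intervals per band and a less favourable headline rate.
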